Study Protocol

Official Title: Poor Sleep and Inflammation in HIV-Infected Adults (SASH)

ClinicalTrials.gov ID (NCT number): NCT03848325

Protocol Date: 7/13/2023

Scientific Background

Background:

Although antiretroviral therapy (ART) has significantly increased the life expectancy of HIV-infected individuals, HIV+ individuals are still at an increased risk of non-AIDS associated chronic diseases such as cardiovascular and pulmonary disease. This increased risk has been associated with persistent immune activation and increased levels of systemic inflammation. Indeed, people living with HIV (PLWH) with higher levels of inflammatory biomarkers have higher hazards of long-term mortality. Furthermore, this chronic inflammation and immune activation has been associated with premature cardiovascular disease and obstructive pulmonary disease. Even with virologic suppression and complete immune reconstitution on ART, PLWH have greater levels of immune activation and persistent inflammation compared to the HIV- population. Poor sleep, a common comorbidity observed among PLWH, may worsen the burden of long-term cardiovascular and pulmonary morbidity since it is also associated with both inflammation and inflammation-related long-term morbidity among HIV- individuals.

We propose a novel mechanistic framework by which acute, sub-acute and chronic sleep disruption may synergistically interact with HIV infection to increase systemic inflammation leading to an increased risk of cardiopulmonary dysfunction. Both, poor sleep acting via reduced expression of adenosine receptors and HIV infection with reduced frequencies of T cells expressing the rate-limiting ectonucleotidase CD73 can lead to reduced adenosine signaling. This loss of the normal immunosuppressive actions of adenosine results in an unregulated inflammatory output predisposing to the long-term cardiovascular and pulmonary complications associated with HIV. The disrupted adenosine signaling may also feedback to perpetuate chronic sleep disruption.

Significance:

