Hypothesis 1: Objectively measured poor sleep is associated with greater levels of inflammation and markers of cardiopulmonary disease among antiretroviral therapy (ART)-treated people living with HIV (PLWH) compared to those without HIV.

Hypothesis 2: Among ART-treated PLWH, downregulation of the adenosine pathway is associated with objectively measured markers of poor sleep.

Hypothesis 3: Acute sleep deprivation in ART-treated PLWH does not produce a compensatory increase in extracellular adenosine generation and signaling, leading to increased inflammation and endothelial dysfunction.

Study Design & Methods

Research Activities:

Recruitment

Individuals with and without HIV will be recruited through advertising in local longitudinal research cohorts studying PLWH, by advertising through clinics that care for PLWH and patients at high risk for developing HIV, and through platforms developed for recruiting people in the community interested in participating in research. Telephone screening will be performed to assess eligibility and review the study protocol. Individuals who meet eligibility criteria and are interested in participating will be scheduled for an in-person study visit.

Cross-Sectional Protocol

Visit 1

A point-of-care urine pregnancy test will be given to women of child-bearing potential. If the pregnancy test is positive, the participant will be ineligible for the study and procedures will be discontinued. The participant will then be asked to complete a battery of interviewer-administered questionnaires. This battery consists of questions on demographics, education, work schedule, caffeine use, nicotine use, and the reduced Morningness Eveningness Questionnaire (rMEQ) to assess circadian preference. Participants will have a wrist actigraph (Respironics Spectrum) placed on the non-dominant wrist and instructed to wear for two weeks. They will be given instructions

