- Atypical sleep patterns (mean sleep duration < 6 hours, sleep efficiency < 85%, standard deviation of sleep duration > 60 minutes, sleep midpoint < 2 a.m., sleep midpoint > 5 a.m.)
- Elevated risk of adverse health effects from sleep deprivation (bipolar disorder, epilepsy, history of suicidal ideation in the past 6 months)
- Heavy caffeine use (>3 caffeinated beverages per day)
- Alcohol abuse
- Drug abuse
- Daily use of medications for treatment of insomnia
- Sleep disordered breathing (AHI >15 on in-lab sleep study)
- Current pregnancy

Statistical Analysis Plan

Hypothesis 1:

The primary exposures will be four domains of sleep health: sleep duration (mean hrs/night during the main rest period), sleep fragmentation index (mean across main rest periods), sleep regularity (interdaily stability over a 14-consecutive day period), and sleep apnea severity (pAHI). Secondary measures will be mean sleep midpoint, mean diary-reported sleep quality, and

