proportion of days with naps. The primary measures of inflammation will be serum IL-6 and sCD14 levels. Secondary measures will include the other 12 cytokines both inflammatory and anti-inflammatory on the Luminex platform including TNF α , CRP, IL-10, and sCD163. All inflammatory biomarkers will be transformed as needed to approximate a normal distribution. Given that some sleep exposures (particularly sleep duration) have U-shaped associations with cardiovascular outcomes, we will initially model sleep exposures in quintiles to assess for non-linear relationships with inflammation measures. If a linear association is confirmed, we will then model sleep exposures continuously to maximize power and use multivariable linear regression to regress IL-6 and sCD14 levels on each of the three sleep exposures among HIV+ subjects. Initial analyses will adjust for age and sex. Alternatively, we will use fractional polynomial regression to test the nonlinear relationship between sleep measures and inflammatory markers. In all models, we will further adjust for CD4+ T cell count and viral load to determine if sleep exposures are associated with inflammation in HIV+ subjects independent of severity of infection. Subsequently, we will generate models including all four sleep exposures simultaneously to understand the independent effects of each sleep domain. If needed, we will apply dimension reduction methods (e.g., principal components analysis) to overcome collinearity in sleep domains. Secondary analyses will utilize structural equation modelling to evaluate the extent to which identified associations represent effects mediated by sleep directly versus effects specific to depression. Furthermore, we will stratify by sex to separately evaluate the association between sleep and inflammation in men and women. Formal testing of effect modification will be performed by including an interaction term in the multivariable models. We will repeat models in HIV- subjects and then test whether HIV infection moderates the association between sleep and inflammation by modeling data from those with and without HIV infection in one model with a sleep by HIV interaction term, using a two-sided $p < 0.05$ as the criterion for rejecting the null hypothesis of no effect modification.

Hypothesis 2:

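### The pooled sleep-by-HIV test names no variance structure; by default it assumes one residual variance for both HIV groups, and its 5% level depends on that assumption

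*Combined protocol and SAP*

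**What the plan says.** The Statistical Analysis Plan, Hypothesis 1, plans to "use multivariable linear regression to regress IL-6 and sCD14 levels on each of the three sleep exposures among HIV+ subjects" when a linear association is confirmed, with fractional polynomials as the alternative. (The number of exposures in that sentence does not bear on this point.) The models are then repeated in HIV- participants. The comparison of the two groups is made by "modeling data from those with and without HIV infection in one model with a sleep by HIV interaction term". The decision rule for that term is given as "using a two-sided $p < 0.05$ as the criterion for rejecting the null hypothesis of no effect modification". No other hypothesis test in the SAP has a stated significance level; the p < 0.10 under Hypothesis 2 only selects confounders.

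On distribution, the same section says: "All inflammatory biomarkers will be transformed as needed to approximate a normal distribution". It does not mention equal variance between HIV groups, robust standard errors, group-specific variances or a variance check. The documents give no HIV+ or HIV- sample size, no ratio between the groups, no biomarker SD and no variance for any sleep measure.

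**The concern.** The interaction coefficient is the difference between two slopes, one per HIV group. Its true sampling variance is the sum of two terms, each using its own group's residual variance. Ordinary least squares on pooled data replaces both with a single weighted average. When the residual variances differ, the average is too small for one group and too large for the other, and the two errors generally do not cancel.

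At stake is the p < 0.05 rule for moderation by HIV. If the standard error is too small, moderation is declared too often when there is none. If it is too large, the test misses moderation that the study is looking for. Transforming biomarkers towards a normal shape may reduce unequal spread but does not ensure equal spread.

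**Working it through.** **Inputs.** From the SAP: alpha 0.05 two-sided, and one pooled linear model. Assumed, because the documents do not give them: group sizes n1 (HIV+) and n2 (HIV-), residual SDs s1 and s2, and exposure variances v1 and v2.

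**Formulas (large sample).**
- True variance of the interaction: Vtrue = s1²/(n1·v1) + s2²/(n2·v2)
- Variance that pooled OLS reports: Vmodel = [(n1·s1² + n2·s2²)/(n1 + n2)] × [1/(n1·v1) + 1/(n2·v2)]
- Actual level = 2 × [1 − Φ(1.96 × √(Vmodel/Vtrue))]

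Subtracting, Vtrue − Vmodel = [(s1² − s2²)/(n1 + n2)] × [n2/(n1·v1) − n1/(n2·v2)]. This is zero if s1 = s2, or if n1²·v1 = n2²·v2. Equal group sizes alone are therefore not enough; the exposure variances must match as well.

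**Step 1, the plan's own figure.** With s1 = s2, Vmodel = Vtrue and the level is 5.0% at 1:1 and at 2:1. Simulation (20,000 runs, age and sex in the model) gives 5.0% at 100/100 and 5.2% at 200/100.

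**Step 2, unequal spread and unequal group sizes.** Set s2 = 1, v1 = v2 = 1 and the smaller group to 1 unit; the scale cancels. For HIV+:HIV- of 1:2 and SD ratio 1.3: Vtrue = 1.69 + 1/2 = 2.190, and Vmodel = [(1.69 + 2)/3] × 1.5 = 1.845. The simulated columns use N = 200 (67/133 or 133/67), 6,000 runs, age and sex in the model, and no true interaction.

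| HIV+:HIV- | SD ratio HIV+/HIV- | Vtrue | Vmodel | √(Vmodel/Vtrue) | Level, formula | OLS simulated | HC3 simulated |
|---|---|---|---|---|---|---|---|
| 1:2 | 1.3 | 2.190 | 1.845 | 0.92 | 7.2% | 7.5% | 5.1% |
| 1:2 | 1.6 | 3.060 | 2.280 | 0.86 | 9.1% | 9.5% | 5.4% |
| 2:1 | 1.3 | 1.845 | 2.190 | 1.09 | 3.3% | 3.1% | 4.5% |
| 2:1 | 1.6 | 2.280 | 3.060 | 1.16 | 2.3% | 2.3% | 4.7% |

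In the last two rows the standard errors are 9% and 16% too large. With milder ratios of 0.8 and 1.25 at 2:1, the formula gives 6.9% and 3.5%.

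**Step 3, equal group sizes but unequal exposure variance.** SD ratio 1.5, 1:1, so the pooled variance is (2.25 + 1)/2 = 1.625.
- v1/v2 = 0.5: Vtrue = 2.25/0.5 + 1 = 5.5; Vmodel = 1.625 × 3 = 4.875; level 6.5% (simulated at 100/100: OLS 6.4%, HC3 4.7%).
- v1/v2 = 2: Vtrue = 2.25/2 + 1 = 2.125; Vmodel = 1.625 × 1.5 = 2.4375; level 3.6% (simulated: OLS 3.7%, HC3 5.0%).

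Across the ten settings of the 20,000-run simulation, OLS ranged from 2.5% to 8.6% and HC3 from 4.6% to 5.3%.

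**Step 4, cost of HC3 if variances are equal.** N = 200, 10,000 runs, true interaction set to (1.960 + 0.842) × √(1/n1 + 1/n2), aiming at about 80% power. At 100/100, power is 78.2% with OLS and 76.4% with HC3. At 67/133 it is 78.1% and 76.2%. The HC3 standard error averages 2-3% larger.

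**The case against.** The strongest reply is that the SAP never states a single residual variance. A pooled model can carry robust errors or group-specific variances, and most regression plans leave this unsaid. That stands: the single variance is the default reading of linear regression in one model, so the point is an omission and not a stated mistake.

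The second reply is that nothing in the documents shows unequal spread. A reader might infer it from the Scientific Background, which says that "PLWH have greater levels of immune activation and persistent inflammation compared to the HIV- population". That is a difference in level, which the HIV main effect absorbs; it says nothing about residual SD. A reader might also point to the inclusion criteria, where HIV- participants need meet only an age range. But the exclusions for sleep disorders, inflammatory disease and immune-active drugs apply to both groups, and the extra HIV+ requirements (48 weeks of ART, CD4 above 200) may narrow the HIV+ group. On the other side, HIV+ entry sets no viral-load limit, so variation due to viral load could widen the HIV+ residual if the pooled model omits it. The documents do not settle the direction.

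Third, inflated false positives need the smaller or less informative group to be the more variable one. Hypotheses 2 and 3 use HIV+ participants only, so an HIV+ majority is at least as plausible as the reverse. If HIV+ were also the more variable group, and exposure variances were similar, the test would be conservative. That stands too, although lost power is still a cost.

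Finally, transformation of skewed markers often reduces unequal spread. That is true, but it does not guarantee equality on the modelled scale. Nor is HC3 exact: at an extreme 50/150 split with SD ratio 1.6, two simulations gave it 5.2% and 5.8%, against 12.0% and 12.7% for OLS.

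**Conclusion.** The point holds as a cheap improvement. As written, the 5% rule for the sleep-by-HIV term is secure under the default analysis only if residual variances are equal, or if group sizes and exposure variances happen to balance (n1²·v1 = n2²·v2). Otherwise the level moves in a direction the documents do not allow one to predict. For N = 200, splits of 1:2 or 2:1, SD ratios of 1.3 to 1.6 and equal exposure variances, it is roughly 2% to 9%; all of these inputs are assumptions.

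Three stronger readings are tempting and not supported. The documents do not show that this trial's false-positive rate exceeds 5%, since they give neither group sizes nor SDs. Equal recruitment of the two groups would not by itself remove the problem, as Step 3 shows. And the argument should not be carried over to the sex-by-sleep interactions, because there is no information on spread or group size by sex.

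**What to change.** In the Statistical Analysis Plan, Hypothesis 1, add that the sleep-by-HIV term will be tested with HC3 standard errors, or in a generalized least squares model with separate residual variances for HIV+ and HIV- participants. Choose one and name it before the data are analysed, so that the standard error is not selected after the p-value is seen. Report the number of HIV+ and HIV- participants in each pooled model.

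This takes one sentence and a software option, with no change to design or data collection. If the variances turn out equal, the price of HC3 at N = 200 is about 2 percentage points of power and intervals 2-3% wider.

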We will compare the frequencies of immune cells expressing ectonucleotidases (CD39+ T cells, CD73+ T cells, and CD39+ CD73+ T cells), monocyte adenosine receptor expression (A1R and A2AR), ADO and inosine levels, and measures of T cell activation between those HIV+ subjects with healthy and poor sleep. Ectonucleotidase expression on B cells and monocytes, additional purine pathway metabolites, and frequencies of CD14+ monocytes expressing IL-6 and/or TNF α will also be compared in secondary analyses. Analyses will initially use t-tests for normally distributed variables or Mann Whitney tests for non-normal distributions. Subsequent analyses will consider potential confounders (age, sex, CD4+ T cell count, viral load, habitual caffeine use, chronotype, sleep midpoint) and adjust in multivariable linear regression for the set of variables that differ between the healthy and poor sleep groups at $p < 0.10$. Sex-related differences will be tested by evaluating the statistical significance of a sex * sleep interaction term.

Hypothesis 3:

The primary outcome measures are levels of soluble CD14, soluble CD163, and circulating IL-6 levels. Secondary outcome measures are flow mediated dilation (percent change in brachial artery diameter to reactive hyperemia), monocyte expression of IL-6, monocyte expression of TNF α , frequency of CD4+ T cells expressing HLA-DR and CD38, and frequency of CD8+ T cells expressing HLA-DR and CD38. Additional pre-specified outcomes include plasma adenosine and inosine levels, urinary 3'5'-cAMP, and frequencies of CD4+ and CD8+ T cells expressing CD39

and CD73. The impact of sleep deprivation will be assessed by performing paired t-tests of each of these outcomes comparing baseline to post-sleep deprivation values. For variables with non-normal distributions, we will either transform variables or use Wilcoxon signed-rank tests. The correlation between the changes in each domain (expressed as percent change from baseline) will be calculated to assess the extent to which change in endothelial function may be predicted by change in inflammation or ADO signaling and change in inflammation by change in ADO signaling. Secondary analyses will consider the extent to which sex, CD4+ T cell count, and viral load impact sensitivity to sleep deprivation by regressing each of these potential effect modifiers on the percent change in each of the primary outcome measures for inflammation, endothelial function, and ADO signaling.

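### Hypothesis 2 compares healthy and poor sleep groups that are never defined, although the same participants have continuous sleep measures that would usually carry more information

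*Combined protocol and SAP*

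**What the plan says.** Study Objectives words Hypothesis 2 as an association: "downregulation of the adenosine pathway is associated with objectively measured markers of poor sleep". The SAP section for Hypothesis 2 turns this into a two-group comparison, covering the adenosine-pathway outcomes and "measures of T cell activation between those HIV+ subjects with healthy and poor sleep".

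The tests come in two steps. First, "Analyses will initially use t-tests for normally distributed variables or Mann Whitney tests for non-normal distributions". Then potential confounders are considered (age, sex, CD4+ count, viral load, caffeine, chronotype, sleep midpoint), and the plan will "adjust in multivariable linear regression for the set of variables that differ between the healthy and poor sleep groups" at p < 0.10. A sex-by-sleep interaction is also planned, without saying which form the sleep term takes.

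The sleep measures are defined only under Hypothesis 1: "The primary exposures will be four domains of sleep health: sleep duration (mean hrs/night during the main rest period), sleep fragmentation index", followed by interdaily stability and pAHI. (One later sentence there counts three exposures; the list and the joint model have four.) That section starts with quintiles because "some sleep exposures (particularly sleep duration) have U-shaped associations with cardiovascular outcomes". If linearity is confirmed, "we will then model sleep exposures continuously to maximize power"; otherwise fractional polynomials are used.

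The only numeric actigraphy cut-offs are in the Aim 3 exclusion criteria: "Atypical sleep patterns (mean sleep duration < 6 hours, sleep efficiency < 85%, standard deviation of sleep duration > 60 minutes", plus limits on the sleep midpoint. Nothing links them to Hypothesis 2.

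**The concern.** There are two separate problems.

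The first is the method. A hypothesis about association with measured markers is addressed directly by regression on those markers. Splitting a measure in two treats participants just either side of the cut as different and all those on one side as alike. The plan itself gives power as its reason for continuous modelling under Hypothesis 1, and gives no reason for departing from it under Hypothesis 2. Supplying a cut-point would remove the ambiguity but not the loss of information.

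The second is the missing definition. Four primary and three secondary sleep measures are available, and sleep questionnaires are also collected at Visit 2. With the measure, the cut and the combination rule all open, the grouping could be settled after its association with the outcomes is visible. The confounder screen inherits the problem, because its covariates depend on the same undefined groups.

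**Working it through.** **Inputs.** The documents give no sample size, effect size, power or split proportion for Hypothesis 2, so there is no planned figure to reproduce. A two-sided 0.05 level appears only for the Hypothesis 1 interaction and is assumed here. Also assumed: one roughly normal sleep measure, a linear association, and a single split with a proportion p on one side.

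**Information retained by a split** = φ(z_p)² / [p(1−p)], where z_p is the normal quantile and φ the normal density.

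- 50/50: 0.3989² / 0.25 = 0.637, a loss of 36%
- 30/70: 0.3477² / 0.21 = 0.576, a loss of 42%
- 20/80: 0.2800² / 0.16 = 0.490, a loss of 51%

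**Power after the split** = 1 − Φ(1.96 − δ√info), with δ = 2.80 for 80% and 3.24 for 90% power on the continuous measure.

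| Split | From 80% | From 90% | Sample size multiplier (1/info) |
|---|---|---|---|
| 50/50 | 61% | 73% | 1.57 |
| 30/70 | 57% | 69% | 1.74 |
| 20/80 | 50% | 62% | 2.04 |

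**Cross-check with Fisher's z.** For assumed correlations of 0.2, 0.25 and 0.3, the continuous analysis needs N = 194, 124 and 85 for 80% power. At those sizes a median split has about 60% power and a 20/80 split about 49%. Regaining 80% needs N = 306, 196 and 135 with a median split, or 399, 255 and 176 with a 20/80 split.

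**Outside those assumptions.**

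- Extreme groups with the middle left out retain 2φ(z_p)²/p of the information, where p is the proportion in each outer group. With the outer 20% to 40% on each side, the loss is about 19% to 25%.
- A moderately skewed exposure (gamma, shape 2) loses about 36% to 47%; a strongly skewed one (lognormal, SD 1 on the log scale) about 46% to 73%.
- If the true relation is a step at the cut, the comparison reverses: a linear term keeps only 64%, 58% or 49% of what the group contrast captures.
- For a U-shape, or a composite of several domains, the formula does not apply.

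**Room for choice.** A null simulation (4,000 replicates, n = 100 and 200, one outcome, nominal 5%) gave these rates of at least one significant result:

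- five candidate cut-points on one domain: 16% to 17%
- a median split on any of four independent domains: 17% to 19%
- five cut-points on any of four independent domains: about 50%

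The domains were simulated as independent, so the four-domain rates are upper-end illustrations.

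**Cost of testing four exposures.** Uncorrected and independent, the chance of at least one false positive per outcome is 1 − 0.95⁴ = 19%. With Bonferroni (two-sided 0.0125, critical value 2.50), 80% power becomes Φ(2.80 − 2.50) = 62%, and 90% becomes Φ(3.24 − 2.50) = 77%. If the plan instead split each of the four domains at the median, the same correction would give Φ(2.80 × √0.637 − 2.50) = Φ(−0.26) = 40%.

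**The case against.** The strongest reply is that the loss figure prices one particular definition of groups that the plan has not defined. The Significance section promises a multi-dimensional view of sleep, so healthy versus poor may be a composite. That is a different exposure, and four separate models would not reproduce it. The plan also doubts linearity itself, and under a threshold relation the group contrast would be the better one. This stands: the percentages are conditional.

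Second, continuous modelling under Hypothesis 1 depends on linearity being confirmed, and Hypothesis 2 does not end with the unadjusted tests. Both are true, and they soften the contrast between the two sections. They do not remove it. Hypothesis 1 keeps a flexible continuous form when linearity fails, and the Hypothesis 2 regression states no continuous sleep term and screens its covariates on the groups.

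Third, four exposures per outcome bring multiplicity. Bonferroni takes 80% power to about 62%, nearly the 61% of a single pre-specified median split. This also stands, so the change needs a multiplicity rule and its gain should not be oversold. The same burden would fall on the plan if each domain were split.

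Finally, a reader might infer that the grouping will be, or was, chosen to suit the results. The documents do not support that. They show an opportunity only, and writing the rule down in advance would close it.

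**Conclusion.** The concern holds in conditional form. It is clear from the text that the groups are undefined and that no continuous-exposure analysis is specified for Hypothesis 2. For one roughly normal measure, a linear association and a single split between 50/50 and 20/80, the two-group method loses about 36% to 51% of the information and takes 80% power to about 61% to 50%. Confidence in that size is moderate, because the split, the distribution and the shape of the association are all assumptions.

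A reader might infer that the plan necessarily discards a third to a half of the information for every outcome. The documents do not support this: the loss is smaller for extreme groups, may be larger for skewed measures, and is not measured by this formula for a U-shape, a threshold or a composite. The point is worth acting on because the data for the better-specified analysis are already being collected.

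**What to change.** 1. Make the main Hypothesis 2 analysis a regression of each adenosine-pathway measure on the four continuous Hypothesis 1 exposures. Use the same functional-form check (linear or fractional polynomial), and adjust for the listed confounders rather than for those that pass a screen on the groups.
2. Control for the four exposures per outcome, for example by a joint test of all four or a Holm correction.
3. Keep the healthy versus poor contrast as a secondary analysis. State its measure, cut-point, rule for combining domains and handling of any middle group before biomarker data are linked to the sleep data.
4. Say which form of sleep enters the sex interaction.

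The cost is SAP wording and more models per outcome; no new data are needed. Multiplicity control gives back part of the power gain, and a flexible functional form uses extra degrees of freedom that the power figures above do not count.

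### Hypothesis 2 lets a p < 0.10 imbalance test choose which of seven listed confounders are adjusted for, so a real confounder can be left out; the covariates should be fixed in advance

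*Combined protocol and SAP*

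**What the plan says.** In the SAP under Hypothesis 2, adenosine-pathway markers are compared, "and measures of T cell activation between those HIV+ subjects with healthy and poor sleep". The first step is an unadjusted two-sample test (t-test or Mann-Whitney). The second step considers "potential confounders (age, sex, CD4+ T cell count, viral load, habitual caffeine use, chronotype, sleep midpoint" and will "adjust in multivariable linear regression for the set of variables that differ between the healthy and poor sleep groups at" p < 0.10. No covariate is forced into the model, the covariate's relation to the outcome plays no part, and no model with all seven is planned. Sex also appears in a separate sex-by-sleep interaction test, which does not place it in the main adjusted comparison.

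Under Hypothesis 1 the approach differs. There, "Initial analyses will adjust for age and sex", and then "In all models, we will further adjust for CD4+ T cell count and viral load". No significance test decides whether these four variables enter. That text concerns the inflammation models and does not carry over to Hypothesis 2.

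**The concern.** The Study Objectives describe Hypotheses 1 and 2 as a cross-sectional evaluation, so randomisation does not balance the sleep groups and adjustment is the only control of confounding. Confounding bias is the product of two things: how far the groups differ on a covariate, and how strongly that covariate predicts the outcome. The p < 0.10 rule looks only at the first, and through a test whose power depends on group size. In small groups a covariate with a real imbalance and a real effect will often fail the screen.

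The adjusted sleep–adenosine estimates could then keep part of the confounding the plan set out to remove, and the covariate set would not be known until the data are seen. The same four variables are fixed under one hypothesis and left to a significance test under the next, with no reason given.

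**Working it through.** The documents state no sample size, group size, imbalance or effect size for Hypothesis 2, so there is no planned figure to reproduce. All inputs below are assumptions: equal groups of 25, 50, 100 or 150; a true imbalance of 0.3 SD per confounder; an outcome slope of 0.3 per SD; independent normal confounders; within-group outcome variance of 1; and no true sleep effect.

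**Step 1: chance that a confounder passes the screen.** The two-sample t statistic is noncentral t with 2n − 2 degrees of freedom and noncentrality 0.3 × √(n/2), that is 1.06, 1.50, 2.12 and 2.60. Against two-sided 10% critical values of 1.68, 1.66, 1.65 and 1.65, the pass probability is 28%, 44%, 68% and 83%. The confounder is therefore dropped in 72%, 56%, 32% and 17% of samples.

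**Step 2: how much one omission can matter.** A dropped covariate has an observed imbalance below about 1.66 × √(2/n). Omitting it shifts the estimate by at most 0.3 × 1.66 × √(2/n) ≈ 0.5 × √(2/n). Since √(2/n) is the standard error of the unadjusted difference, each omission costs at most about half a standard error. Omissions in the same direction add up; omissions in opposite directions partly cancel.

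**Step 3: bias and type I error under the screen** (simulation, 2,000 to 4,000 replicates per cell; Monte Carlo error about 0.35 to 0.5 points at 5%).

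| Confounders acting | Unadjusted bias (SD) | Bias left by the screen, n = 25 / 50 / 100 / 150 | Type I error |
|---|---|---|---|
| One | 0.3 × 0.3 = 0.09 | about 0.04 / 0.03 / 0.015 / 0.01 | about 5–6% |
| Three, five or seven, alternating signs | 0.09 (net) | at most about 0.04 / 0.03 / 0.02 / 0.01 | about 3–6% |
| Three, same direction | 3 × 0.09 = 0.27 | 0.11–0.12 / 0.08 / 0.04 / 0.02 | about 5–6% |
| Five, same direction | 5 × 0.09 = 0.45 | 0.19 / 0.14 / 0.07 / 0.03 | about 6–10% |

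Adjusting for all the simulated confounders gave bias near zero and type I error near 5%.

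**Step 4: the replacement tested against its own weak point.** Suppose all seven listed variables are true confounders in the same direction, an extreme case. A model with five covariates leaves out chronotype and sleep midpoint, so its bias is 2 × 0.3 × 0.3 = 0.18 SD at every group size, with type I error of about 12/20/37/51%. The screen leaves 0.27/0.19/0.10/0.05 SD with about 13/16/12/8%. The five-covariate model then has the higher type I error from 50 per group and the larger bias from 100 per group. Adjusting for all seven removes the bias.

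**Step 5: precision cost of fixed covariates.** If p covariates are unrelated to the outcome but imbalanced by 0.3 SD, the standard error grows by √[(N − 3)/(N − 3 − p) × (1 + p × 0.09/4)], with N the total. For p = 5 and N = 50: √(47/42 × 1.1125) = 1.12. Over the four group sizes the increase is 12/8/7/6% for five covariates and 17/12/10/9% for seven.

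**The case against.** The strongest reply is that the harm depends on confounders lining up. The documents give no signs, and with alternating signs the screen leaves 0.04 SD or less and type I error of about 3–6%. Even three in the same direction barely move the error rate, and each dropped covariate can shift the estimate by only about half a standard error. This stands, and it limits the size of the point. A reader might infer that the rule invalidates the Hypothesis 2 tests or pushes false positives into double digits. The documents do not support that: among the cases examined, such rates appear consistently only when all seven confounders act independently in the same direction. Chronotype and sleep midpoint both describe sleep timing and are unlikely to be independent.

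A second reply is that the rule is at least mechanical, with its list and threshold written in advance, and that it beats no adjustment. Both are true. They do not answer the fact that the rule ignores the outcome, or that Hypothesis 1 manages without it.

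A third reply is that a fixed five-covariate model is not always better. Step 4 shows that this is right. It is the reason to report a seven-covariate model as well, and to say which model is primary.

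A reader might also count the missing definition of healthy and poor sleep as evidence here. That is a separate gap with its own remedy; it says nothing about whether a p < 0.10 screen is a sound way to choose covariates.

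**Conclusion.** The point holds as a weakness in method whose practical harm is modest in most settings. The screen can drop a real confounder, nothing elsewhere in the documents fixes the Hypothesis 2 covariates, and a better rule is already used under Hypothesis 1. The residual bias is at most about 0.04 SD with one confounder or mixed signs. It reaches about 0.1 to 0.2 SD only in small groups with three to five confounders aligned, and type I error then stays below about 10%. These sizes rest entirely on the assumed 0.3 SD imbalance, slope of 0.3, independence and 25 to 150 per group; the plan's true values are unknown. The change is worth making because it is cheap and settles the covariate set before the data are seen.

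**What to change.** Delete the p < 0.10 rule and name the following in the SAP before analysis.

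- **Primary adjusted model:** age, sex, CD4+ count and viral load, as in Hypothesis 1, plus habitual caffeine use.
- **Sensitivity model, reported beside it:** the same covariates plus chronotype and sleep midpoint. The SAP lists midpoint among its sleep exposures under Hypothesis 1 ("Secondary measures will be mean sleep midpoint"), so adjusting for it may remove part of the exposure. Leaving both variables out could leave more bias than the screen if they are true confounders. Call neither model unbiased, and call an association robust only if the two agree.
- **Primary model without caffeine:** caffeine use may follow from poor sleep. If so, adjusting for it would remove about 0.3 × 0.3 = 0.09 SD of the effect at the assumed strengths.

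The cost is SAP wording. All seven variables are already on the plan's list, and caffeine use is already asked about at Visit 1 ("This battery consists of questions on demographics, education, work schedule, caffeine use, nicotine use"). If the covariates do not predict the outcome and are imbalanced by 0.3 SD, standard errors widen by about 6–12% with five covariates and 9–17% with seven. The cost is higher if midpoint differs strongly between the groups, because each covariate adds a quarter of its squared standardised imbalance to the variance factor in Step 5.
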